### 6.3.6.2 Handling of Dropouts or Missing Data

Missing data for atrophic acne scar counts will be imputed using Multiple Imputation (MI) under the Missing At Random (MAR) assumption. The following steps will be followed:

- 1. The missing data pattern of atrophic acne scar counts will be evaluated. If the pattern is non-monotone, the MCMC method of SAS PROC MI will be used to make it monotone. The single chain method will be used, with 200 burn-in iterations and 100 iterations between imputations. In case of lack of convergence with the single chain method, the multiple chain method will be used. Separate imputations by treatment group will be carried out. The minimum values for imputed variables will be set to 0, in order to force PROC MI to redraw another value for imputation when an intended imputed value is less than the 0. Imputed values will be rounded to the nearest integer. The seed number will be set to 202395 and fifty (50) imputations will be created.
- 2. SAS PROC MI will be used for imputing missing values of data with monotone missing pattern. If the MCMC method of step 1 was previously employed, one imputation will be made using each of the fifty (50) MCMC-imputed datasets. If the MCMC method of step 1 was not previously employed, fifty (50) imputations will be created assuming the data are Missing At Random. The seed number will be set to 202395. A linear regression model will be used with covariates for non-missing atrophic acne scar counts from earlier scheduled time points

including baseline. In case of lack of convergence with linear regression model, a predictive mean matching method will be used. Separate imputations by treatment group will be carried out. The minimum values for imputed variables will be set to 0, in order to force PROC MI to redraw another value for imputation when an intended imputed value is less than the 0. Imputed values will be rounded to the nearest integer. Absolute and percent change from baseline in atrophic acne scar counts will be derived from the corresponding imputed lesion counts.

- 3. The imputed datasets will be analyzed as specified in sections 6.3.3 and 6.3.5.
- 4. The resulting analysis on the imputed datasets will then be combined to produce a single set of statistics using PROC MIANALYZE.

The number of fifty (50) imputations was selected in order to prevent a power falloff due to choosing a number of imputations too small [1].

As sensitivity analysis of the primary endpoint, the primary analysis will be repeated on the ITT population by imputing atrophic acne scar counts on the basis of a Jump-to-Reference (J2R) approach under the Missing Not At Random (MNAR) assumption. Missing values of bilateral difference in atrophic acne scar counts between the trifarotene side and the vehicle side will be imputed as zero (0).

As additional sensitivity analysis of the primary endpoint, the primary analysis will be repeated on the ITT population by imputing missing data using Last Observation Carried Forward (LOCF). In case no post-baseline value is available, baseline value will be carried forward.

Missing values of acne lesion counts, SGA scores and IGA scores will be imputed using LOCF. In case no post-baseline value is available, baseline value will be carried forward. SGA/IGA success will be calculated from the imputed ordinal SGA/IGA scores. Moreover, SGA/IGA success will be imputed using Missing as Failure (MAF) method as additional analysis.

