### Notes:

- 1) Scar severity grading (SGA) and scar counts will be performed separately. The scar severity assessment will be performed before the scar counting.
- 2) Acne severity grading (IGA) and acne lesion counts will be performed separately. The acne severity assessment will be performed before the acne lesion counting.

[figure not shown]
Throughout the study when possible, the same evaluator should perform the SGA, scar counts, IGA and acne lesion counts, for each subject. In the event there is a change in the assigned evaluator for a given subject, the reason for change should be documented. If it is not possible to use the same evaluator to follow a given subject, evaluations between the primary and subsequent evaluator should overlap (both evaluators should examine the subject together and discuss findings) for at least one prior visit. At the final study visit (Week 24 or Early Termination), attempts should be made for the rater to be the same as baseline for the following assessments, to the extent possible:

[figure not shown]

[figure not shown]
For all efficacy assessments, the zone in the middle of the face (approximately 2 cm wide and inclusive of the nose) should be excluded for clinical efficacy evaluation because subjects may apply a mix of investigational products in this area (Figure 2).

1.0

Study Number 202395 CONFIDENTIAL Page 24 of 59
Statistical Analysis Plan Final version 2.0, 27FEB2023

[figure not shown]

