### 4 SAMPLE SIZE CONSIDERATION

The sample size calculation is based on the results of the study RD.06.SPR.118295 "A Multi-Center Study to evaluate Subject Reported Outcomes with use of trifarotene 50  $\mu$ g/g cream in the treatment of moderate facial and truncal acne vulgaris" and of the study RD.03.SPR.105061 "Effect of Adapalene 0.3% - Benzoyl Peroxide 2.5% gel versus vehicle gel on the risk of formation of atrophic acne scars in moderate to severe acne subjects".

In study RD.06.SPR.118295, the following results were obtained for the absolute change from baseline in total atrophic acne scar count at week 24:

These results refer to a whole face treatment whilst in the current study a split-face design is used. Moreover, due to the lack of a Vehicle arm, it is not possible to estimate the mean value and the variability of the difference in mean absolute change from baseline in total atrophic acne scar between treatment arms.

It is possible to hypothesize that the mean reduction in trifarotene 50  $\mu$ g/g cream arm when only half-face is treated is -1.7 but there are no data for estimating the variability of the difference between trifarotene 50  $\mu$ g/g cream and vehicle cream.

In study RD.03.SPR.105061 a split-face design was used and the following results were obtained for the absolute change from baseline in total atrophic acne scar count at week 24:

CCI

Under the following hypotheses:

- Mean absolute change from baseline in total atrophic acne scar count at week 24 for trifarotene 50 μg/g cream is -1.7
- Mean absolute change from baseline in total atrophic acne scar count at week 24 for Vehicle cream is zero
- Difference absolute change from baseline in total atrophic acne scar count at week 24 between trifarotene 50 μg/g cream and vehicle cream is -1.7
- Variability of the difference between trifarotene 50 μg/g cream and vehicle cream is 6.0 (derived by supposing an increase of about 35% of the variability observed in study RD.03.SPR.105061)

the sample size for a Student's t-test for paired samples can be calculated according to the following formula:

$$n \ge \frac{\left(t_{\frac{1-\alpha}{2},n-1} + t_{1-\beta,n-1}\right)^2 \sigma_{Diff}^2}{\left(\mu_{Trifarotene} - \mu_{Vehicle}\right)^2}$$

where  $t_{p,v}$  is the Student's t distribution quantile with v degrees of freedom and probability p (n is rounded up to the closest integer).

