**Table 8 Sample Size Calculation** 

α (2-sided)	β	Power (%)	μ Trifarotene - μ Vehicle	♂ Diff	n	Drop-out and Non-evaluable Proportion (%)	Subjects to be Randomized
0.05	0.2	80	-1.7	6.0	100	15	118

An initial number of 118 subjects is planned to be randomised. Due to the uncertainty of the estimation of the variability, a blinded sample size re-estimation will be performed after 40 subjects complete/discontinue the study (i.e. after 33% of the initial planned subjects complete/discontinue the study) in order to evaluate the need for additional subjects to be randomized.

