### 6.3.3 Analysis of Primary Endpoint

The hypothesis test for the primary endpoint can be formally defined as follows:

$$\begin{cases} H_0: \mu_{Diff} = 0 \\ H_a: \mu_{Diff} \neq 0 \end{cases}$$

where  $\mu_{Diff}$  is the mean of the differences in change from baseline in total atrophic acne scar count at Week 24 between the trifarotene 50  $\mu$ g/g side and the vehicle side.

The hypothesis test for the primary endpoint will be evaluated on the ITT population at the two-sided significance level  $\alpha = 0.05$ . Efficacy will be claimed if the between treatment difference on the primary endpoint is statistically significant with a p-value < 0.05.

The bilateral difference between the trifarotene side and the vehicle side in absolute change from baseline in total atrophic acne scar counts at Week 24 will be analyzed on the ITT population using the Student's t-test for paired samples. The point estimate of the mean difference and the related 95% confidence interval will be presented. Assumption of normality will be checked. If normality assumption is not met, the appropriate non-parametric statistical method (Wilcoxon signed rank test, Hodges-Lehmann estimate of location shift and asymptotic confidence interval) will be used.

For analysis of change from baseline in total atrophic acne scar counts to Week 24, missing counts will be imputed using Multiple Imputation (MI) under the Missing At Random (MAR) assumption. It is expected that the pattern of missing data will be monotonic, with slight deviations being corrected by the Markov Chain Monte Carlo (MCMC) method of the SAS MI procedure. Separate imputations by treatment group will be carried out. Linear regression will be employed to model the missing acne counts, with the following covariates included in the imputation model: non-missing total atrophic acne scar counts from earlier time points (see Section 6.3.6.2 for further details).

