### CONFIDENTIAL

Page 58 of 59 Final version 2.0, 27FEB2023

■ Bottom: 2.0 cm (i.e. footers at 2.0 cm from page edge)

Left: 0.8 cmRight: 0.8 cm

Courier New, 8-point font will be used for TLF contents (excluding column headers) and TLF footnotes.

Courier New, 8-point, bold font will be used for page headers and footers, TLF title, TLF headers, column headers and figures' axis labels.

A clear, accurate and complete programming code will be developed to generate the statistical analyses, summary tables, figures and listings to be integrated in the report. Fluent use of precise titles and footnotes will be made to improve the understanding of summaries and document any assumption. Details of analysis specifications including but not limited to the SAS code will be documented on the shells.

The final list of tables, figures and listings and their shells for the reporting of this study will be available in a separate document that will be developed and will be finalized before database lock.

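### Imputing the two half-faces separately drops residual same-visit correlation from a paired primary analysis; if that correlation is positive, the primary SE and CI are too wide, by an amount the documents do not determine

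*SAP*

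**What the plan says.** SAP 6.3.3 makes the primary analysis a paired t-test on the trifarotene-minus-vehicle difference in change from baseline at Week 24, in all randomized subjects. Missing counts are multiply imputed under MAR, with "the following covariates included in the imputation model: non-missing total atrophic acne scar counts from earlier time points". SAP 6.3.6.2 gives the steps. Both the MCMC step and the monotone regression step carry the instruction "Separate imputations by treatment group will be carried out", with 50 imputations combined by Rubin's rules. SAP 6.3.5.1 repeats the scheme for the intermediate visits. No opposite-side predictor is listed, and no later step restores the pairing before the difference is taken.

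Protocol 7.4.3.3 specifies MI under MAR but does not ask for a split by treatment.

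On the quantities that govern the size of the effect, SAP section 4 concedes that "there are no data for estimating the variability of the difference" between the creams. It takes 6.0 as the SD of the difference, "derived by supposing an increase of about 35% of the variability observed" in another study. The 15% in Table 8 is labelled "Drop-out and Non-evaluable Proportion". No between-side correlation is given.

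**The concern.** Imputing within treatment group suits a parallel-group trial, where the groups are different people. Here each subject supplies both sides, and a missed visit normally removes both counts at once. Two independent draws then replace two counts that may move together. What each side's own earlier counts predict is retained, so a subject with many scars on both sides still gets high imputed values on both. What is lost is any correlation between the sides at the same visit beyond that history.

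If this residual correlation is positive, imputed differences vary more than real ones. The completed-data variance and the between-imputation variance both rise, and the primary SE and CI become too wide. The design relies on the two sides being alike, so the imputation would give back part of the precision that pairing buys. The trial is sized at 80% power, which leaves little slack.

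**Working it through.** **Plan's own figure.** SAP formula with difference 1.7, SD 6.0, two-sided 0.05 and 80% power: (1.984 + 0.845)² × 36 / 2.89 = 99.7, so n = 100. Then 100/0.85 = 117.6, so 118 randomized. Both reproduce.

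**Assumed correlations.** The documents give none. A rough range comes from the whole-face SD of 9.48 (Protocol 7.2) and the SD of the difference, assuming equal side variances:
- SD 6.0: (89.87 − 36)/(89.87 + 36) = 0.43.
- SD before the 35% increase, 6.0/1.35 = 4.44: (89.87 − 19.75)/(89.87 + 19.75) = 0.64.

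Each value joins two different studies, and each is a marginal correlation of changes, not the residual one. They are illustrations only.

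**Closed form for the worst timing.** Let a fraction f have baseline only, with change unrelated to baseline, and let r be the residual correlation. Each side's change has variance 36/[2(1 − r)], so two independent draws differ with variance 36/(1 − r). Rubin's total variance is then

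- separate sides: (36/N) × [(1 − f) + f/(1 − r) + f/((1 − f)(1 − r))]
- pair kept: (36/N) / (1 − f)

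At f = 0.15 and r = 0.43 the bracket is 0.85 + 0.2632 + 0.3096 = 1.4228, against 1/0.85 = 1.1765. The variance ratio is 1.209, so the SE is +10%. At r = 0 both are 1.1765 and there is no excess. At r = 0.2 the excess is +3%, and at 0.64 it is +22%. At f = 0.05 and r = 0.43 it is +4%.

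**Simulation with dropout spread over visits.** Baseline plus eight visits on both sides, N = 118, SD of difference 6.0, monotone dropout, Bayesian sequential regression, Rubin's rules. Set-up A: change is a persistent part plus visit noise (half each), both parts correlated r between sides, 50 imputations, 1,200 to 3,000 trials. Set-up B: visit autocorrelation 0.8, rounding and redraw below zero, 20 imputations, 600 trials.

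| Missing | r | A: SE separate / joint | A excess | B: SE separate / joint | B excess |
|---|---|---|---|---|---|
| 15% | 0 | 0.594 / 0.604 | none | 0.603 / 0.614 | none |
| 15% | 0.43 | 0.640 / 0.602 | +6% | 0.660 / 0.615 | +8% |
| 15% | 0.64 | 0.701 / 0.603 | +16% | 0.721 / 0.612 | +18% |
| 5% | 0.43 | 0.581 / 0.567 | +2% | 0.589 / 0.574 | +3% |

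(The B excess is the run's own ratio, which can differ slightly from the quotient of the two mean SEs.)

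**Calibration at r = 0.43, 15% missing.** In B the separate-side SE averaged 0.660 while the estimate's actual SD was 0.619. Joint imputation gave 0.615 against 0.614. Type I error under separate imputation was 3.2% (A) and 3.8% (B). Power in A was 77% separate against 80% joint.

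**Where the effect shrinks.** If same-visit fluctuations of the two sides are independent, A gives 0.603/0.598 or 0.636/0.627, about +1%. If in addition only Week 24 is missing, it gives 0.586/0.590 or 0.620/0.624, which is no excess. In B, with a marginal correlation of 0.56 but none residual, the ratio was 0.99.

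**The case against.** The strongest defence is that the correlation that matters is undocumented and may be small. Only the residual part counts, and 0.43 and 0.64 are marginal values. The SAP's note that, when possible, "the same evaluator should perform the SGA, scar counts, IGA and acne lesion counts, for each subject" does not establish visit-specific shared error: a stable rater effect is already in each side's baseline and earlier counts. Shared day effects remain plausible but unmeasured. This stands, and it is why the size is given only as a range.

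The missing fraction may also be well under 15%. Table 8 combines drop-out with non-evaluable subjects, and SAP 3.2.4 encourages subjects who stop study drug to keep attending so that primary endpoint data are collected. This stands too; at 5% missing and 0.43 the SE excess is only +2 to +3%.

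The error is conservative, and the observed-case and jump-to-reference analyses do not share it. That is correct. It limits the consequence, but a primary CI that is systematically too wide is still wrong.

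A reader might add that the SAP contradicts itself by keeping the pair elsewhere. That carries little weight. The blinded re-estimation imputes squared left-right differences because the treated side is unknown, and the jump-to-reference analysis simply sets missing differences to zero.

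**Conclusion.** The mechanism is certain and the size is not. Separate-side imputation does not match the paired test. Whenever the residual same-visit correlation is positive, the primary SE and 95% CI are too wide and some power is lost, while the mean difference is essentially unbiased. The illustrative sizes rest on assumed correlation, visit stability, dropout timing and missing fraction, with an SD of the difference of 6.0. The same applies to the intermediate visits in SAP 6.3.5.1, to the extent that counts are missing there.

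Three stronger readings are tempting and not supported:

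- **A power loss at 0.64.** That correlation comes from an SD of 4.44. Pairing it with 6.0 gives a half-face variance of 36/(2 × 0.36) = 50 and a whole-face SD of √(2 × 50 × 1.64) = 12.8, not the documented 9.48. Only the SE ratio can be used at 0.64.
- **That imputing is always less precise than the observed-case analysis.** It can be: in set-up A at 0.43 with dropout spread over visits, the SE is 0.640 against 0.597 for completers. If only Week 24 is missing and counts are stable between visits, it is 0.594 or 0.568, below 0.597. The comparison depends on timing.
- **That the fixed seed makes the SE too small.** The SAP says "The seed number will be set to 202395" but does not describe two runs that reuse the same draws, and it leaves code to the shells ("Details of analysis specifications including but not limited to the SAS code will be documented on the shells"). No conclusion follows from this.

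The imputation should be corrected before unblinding, as a matter of precision and correct coverage. It is not a threat to validity.

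**What to change.** In SAP 6.3.3, 6.3.5.1 and both imputation steps of 6.3.6.2, replace the separate-imputation sentence for scar counts with wording such as:

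*Scar counts will be imputed from one record per subject, with the trifarotene-side and vehicle-side counts at each visit as separate variables, in a single PROC MI run ordered by visit. Any MCMC step will include both sides. In the monotone regression step each count is predicted from the earlier counts of both sides, including baseline; the second side at a visit is also predicted from the first side's count at that visit.*

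The same-visit predictor is what keeps the residual correlation. No new data are needed. Since Protocol 7.4.3.3 does not require the split, a SAP update appears to be enough.

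The cost is a larger model: nine time points on two sides make 18 variables, so up to 17 predictors with about 100 complete subjects (118 × 0.85). A reduced predictor set may be pre-specified in case the full model is unstable. In set-up A at 0.43, a set of at most seven (baseline and the two preceding visits of both sides, plus the same-visit count) gave an SE of 0.604 against 0.602 for the full model. If the sides are in fact uncorrelated, joint imputation widens the SE by about 2% (0.604 against 0.594).

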5.3.2 Inclusion Criteria

Subjects must fulfill inclusion criteria to participate in the study:

- 1. Male or female subject aged 17 to 35 years inclusive, at Screening visit.
- 2. Subject with clinical diagnosis of acne vulgaris on the face as defined by (excluding the nose and middle zone of approximatey 2 cm):

CCI

- 3. Subject with a symmetrical number of the following lesions/scars on the whole face (i.e., there are no more than twice as many lesions/scars of each type on one half of the face than on the other half):
 - a. Inflammatory and non-inflammatory lesions; and
 - b. Atrophic acne scars (minimum of 4 scars per half-face)
- 4. The subject is a female of non-childbearing potential (premenarchal or postmenopausal [absence of menstrual bleeding for 1 year prior to Screening, without any other medical reason], hysterectomy or bilateral oophorectomy).

5. The subject is a female of childbearing potential:

- 5.1 Who is willing to undergo UPTs throughout the course of the study, as required.
- 5.2 Who has been strictly abstinent for 1 month prior to Screening and agrees to continue for the duration of the clinical study and at least 1 month after the last study drug application, OR

Who agrees to use highly effective and approved contraceptive method(s) for the duration of the study and at least 1 month after the last study drug application.

Highly effective methods of contraception include:

- a. bilateral tubal ligation;
- b. approved combined oral contraceptives (estrogens and progesterone), implanted or injectable contraceptives, or hormonal contraceptive vaginal rings with a stable dose for at least 1 month prior to the Screening visit;
- c. intrauterine device or intrauterine hormonal-releasing system inserted at least 1 month prior to the Screening visit;
- d. vasectomized partner for at least 3 months prior to the Screening visit

Note: This criterion applies to a prepubertal female subject who begins menses during the study.

- 6. If a female of childbearing potential uses oral contraceptives that are also approved for treating acne vulgaris (such as cyproterone acetate and ethinyl estradiol; drospirenone and ethinyl estradiol; norgestimate and ethinyl estradiol; norenthindrone acetate and ethinyl estradiol; etc) the dose should be stable for at least 6 months prior to the Screening visit.

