### 6.3.4 Sensitivity Analysis of Primary Endpoint

To assess the robustness of the primary efficacy results, the following sensitivity analyses will be conducted:

- 1) Jump-to-Reference (J2R) approach under Missing Not At Random (MNAR) assumption, by imputing missing differences between treatments as zero (0);
- 2) Missing data of primary endpoint will be imputed using Last Observation Carried Forward (LOCF);
- 3) Observed Case (OC) analysis;
- 4) Per Protocol (PP) analysis.

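### SAP 6.3.6.2 states the jump-to-reference zero-fill for scar counts, while the primary endpoint is a difference in change from baseline; programmed literally, the rule adds chance noise to that one sensitivity analysis

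*SAP*

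**What the plan says.** The primary parameter in SAP 6.3.3 is the "mean of the differences in change from baseline in total atrophic acne scar count at Week 24" between the trifarotene side and the vehicle side, tested with a paired t-test on the ITT population.

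The J2R sensitivity analysis is described in three places:

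- SAP 6.3.4 lists it among four sensitivity analyses of the primary endpoint, carried out "by imputing missing differences between treatments as zero (0". No scale is named.
- Protocol 7.4.3.4 uses the same wording, again without a scale.
- SAP 6.3.6.2, which sets out missing-data handling in detail, says the primary analysis is repeated with scar counts imputed by J2R, and then: "Missing values of bilateral difference in atrophic acne scar counts between the trifarotene side and the vehicle side will be imputed as zero (0".

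Other text bears on the point. The multiple-imputation steps in SAP 6.3.6.2 derive change from the imputed counts. Protocol 5.3.2, criterion 3, asks for rough symmetry only, meaning "there are no more than twice as many lesions/scars of each type on one half of the face than on the other half", with at least 4 scars on each side. SAP 6.3.6.1 plans no covariate adjustment.

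**The concern.** J2R with a zero-fill is meant to say that a subject with no Week 24 count shows no treatment effect. On the scale of the endpoint, that means a change difference of 0. If zero is instead put in for the Week 24 difference in counts, the sides are assumed to have become equal, whatever they were at baseline. A subject who entered with more scars on the trifarotene side is then recorded as having benefited, and one who entered with fewer as having been harmed. Neither value reflects treatment or dropout.

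This matters because J2R is the only analysis of the primary endpoint that the plan labels as missing not at random. Its purpose is to show whether the primary result survives a conservative view of dropout, and noise from baseline asymmetry blurs that answer. With no covariate adjustment planned, nothing later removes the imbalance.

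**Working it through.** **Plan's own figure.** SAP Table 8 gives alpha, beta, power, difference, SD, n, drop-out and N as "0.05 0.2 80 -1.7 6.0 100 15 118". The paired-t formula n >= (t(0.975, n-1) + t(0.8, n-1))^2 x 6.0^2 / 1.7^2 is first satisfied at n = 100, and 100 / 0.85 = 117.6, rounded up to 118. The figure reproduces and is not in question. It supplies the inputs below: N = 118, 118 - 100 = 18 missing, SD 6.0, and a difference of -1.7 (SAP section 4 sets the trifarotene change at -1.7 and the vehicle change at zero).

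**Algebra.** Let T and V be the trifarotene-side and vehicle-side counts, at baseline (0) and Week 24 (24). The endpoint for one subject is

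D = (T24 - T0) - (V24 - V0) = (T24 - V24) - (T0 - V0).

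- Zero on the change scale: D = 0.
- Zero on the count scale: T24 - V24 = 0, so D = -(T0 - V0).

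| Baseline T0 vs V0 | Count-scale fill | Change-scale fill |
|---|---|---|
| 8 vs 4 | -4 | 0 |
| 4 vs 8 | +4 | 0 |
| 14 vs 10 | -4 | 0 |
| 20 vs 10 | -10 | 0 |
| equal sides | 0 | 0 |

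All the unequal pairs are within the 2:1 limit. The SAP's own LOCF rule gives a useful contrast: with no post-baseline value, baseline is carried forward and D = 0. For an 8 vs 4 subject with no post-baseline count, LOCF would give 0 and literal J2R would give -4.

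**Effect on the estimate.** Both fills have the same expectation, -1.7 x 100/118 = -1.44, because randomized sides make the mean baseline difference zero. The count-scale fill adds a random shift with SD = sqrt(18) x b / 118, where b is the SD of the baseline side difference. The documents do not give b; the range is assumed.

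- b = 3: 4.243 x 3 / 118 = 0.11 scars
- b = 4: 4.243 x 4 / 118 = 0.14 scars
- b = 5: 4.243 x 5 / 118 = 0.18 scars

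Against the planned 1.7, that is 6% to 11%.

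**Effect on power.** With a missing fraction of 0.15, the variance of the filled variable is 0.85 x 36 + 0.15 x 0.85 x 1.7^2 + 0.15 x b^2 = 30.97 + 0.15 b^2. The change-scale fill has no b term.

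| Fill | Variance | SD | Power, N = 118 |
|---|---|---|---|
| change scale | 30.97 | 5.57 | 79.9% |
| count scale, b = 3 | 32.32 | 5.69 | 78.2% |
| count scale, b = 4 | 33.37 | 5.78 | 76.9% |
| count scale, b = 5 | 34.72 | 5.89 | 75.2% |

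**How often the two fills disagree.** The simulation used 20,000 trials per setting, with 18 of 118 missing at random and total SD 6.0. The change difference was given either no dependence on the baseline difference or an assumed slope of -0.3; this choice barely mattered. The fills differ on p<0.05 in about 5%, 7% and 9% of trials for b = 3, 4 and 5 at a true difference of 1.7, and in 7-12% at 1.2. At b = 2 the figures are 3% and 5%. At b = 5 and a difference of 1.7, the count-scale fill loses significance in about 7% of trials and gains it in about 2%.

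**The case against.** The strongest reply is that the sentence in 6.3.6.2 is shorthand. It follows a statement that the primary analysis is being repeated, and that analysis concerns change from baseline. SAP 6.3.4 and Protocol 7.4.3.4 put the zero on the treatment difference under a heading about the primary endpoint. The SAP is loose with such terms elsewhere, writing of acne counts or lesion counts where scar counts are meant. Section 8 also promises shells documenting the analysis specifications, finalized before database lock, and these may settle the scale.

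Much of that stands. A reader might infer that 6.3.4 and 6.3.6.2 contradict each other. The documents do not show this: 6.3.4 names no scale, and reading it as change is an inference from its heading and from 6.3.3. What exists is an ambiguity that no passage resolves.

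The literal reading is still realistic. The same paragraph says that counts are imputed, and the section derives change from imputed counts. SAP 4.1 uses similar wording for left-right differences in counts and includes baseline among the covariates. A change difference is zero at baseline by definition, so that usage makes sense only for counts.

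A reader might also infer that every dropout is credited in favor of trifarotene. That is not supported either. Only subjects without a Week 24 count and with unequal baseline sides are affected. The sign goes either way, and randomization makes its expectation zero. Subjects who stop drug early are encouraged to stay for primary-endpoint data, which may keep the number small.

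**Conclusion.** The point holds as a scale ambiguity with a small cost. If 6.3.6.2 is programmed as written, J2R no longer imputes a zero treatment effect. The expected estimate stays at -1.44, the random shift has an SD of 0.11 to 0.18 scars, and power of this check falls by about 1 to 5 points. The significance verdict differs from the change-scale version in about 5-9% of trials at a true difference of 1.7. These sizes rest on 18 of 118 missing, the plan's SD of 6.0, and an assumed baseline side-difference SD of 3 to 5 scars.

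It would be wrong to read this as a threat to the trial's conclusion. The efficacy rule is "Efficacy will be claimed if the between treatment difference on the primary endpoint is statistically significant with a p-value < 0.05", and that test uses multiple imputation of counts, not J2R. The LOCF, observed-case and per-protocol analyses, the multiplicity procedure and the sample size are unaffected. This is a worthwhile clarification of low severity.

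**What to change.** In SAP 6.3.6.2, state that the quantity set to zero is the trifarotene-minus-vehicle difference in the Week 24 change from baseline in total scar count, which is the variable tested in 6.3.3. Put the same wording in 6.3.4, so that both sections name the scale. The cost is one phrase in each section of the SAP. No new data, analysis or sample-size work is needed. The shells should carry the same definition.
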